6.3 Pretreatment workup

- 6.3.1. CT/MRI scan of the chest, abdomen, and pelvis
- 6.3.2. Laboratory evaluation including complete blood count (CBC) with differential, basic metabolic panel (BMP) including creatinine
- 6.3.3. A renal nuclear medicine scan may be obtained prior to radiation treatment or microwave ablation to estimate functional renal parenchymal volume if deemed necessary by the treating physicians.

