6.7 Duration of Therapy

Treatment with SBRT will be delivered over a period of two weeks, with radiation delivered two to three times per week. Four to six weeks after treatment, patients will be evaluated for microwave ablation by the treating radiologist with repeat CT or MRI imaging of the abdomen. Eight weeks after the conclusion of radiation treatment, patients will undergo microwave ablation, a single procedure. Adjuvant systemic treatment will be administered per institutional policies, physician recommendations, and patient preferences. Criteria for removal from study are described below.

6.8 Duration of Follow-Up: Refer to Table 2

After study enrollment, patients will undergo SBRT over a period of approximately 2 weeks. After 8 weeks, patients will undergo microwave ablation. Post treatment, patients will be followed as per standard of care. This will include a clinical visit four weeks after ablation, three months after ablation, six months after ablation, followed by visits every 6 months for a period of 3 years. Imaging will include either contrast-enhanced CT or MRI imaging at 3 and 6 months post therapy and every 6 months for 3 years. A BMP (including creatinine) will be obtained with imaging to evaluate renal function. Long term toxicity (specifically, nephrotoxicity, bowel obstruction, skin changes, and pain) will be assessed at these follow-up visits. Follow-up visits will be conducted by one of the treating physicians (radiation oncologist, interventional radiologist, or urologist) who will document physical exam, laboratory, and imaging findings as well as evaluate for toxicity. Any other evaluations prompted by symptoms, laboratory evaluation, or at the treating physicians' discretion may be performed as per standard of care. If a patient decides to withdraw from the study for non-treatment related reasons, no additional study-specific information will be obtained from the patient's future follow-up visit.

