7.2 Local Control

- 7.2.1. Imaging response will be measured as per the RECIST criteria[17]
 - 7.2.1.1. Complete Response (CR) – Disappearance of entire target lesion
 - 7.2.1.2. Partial Response (PR) – At least a 30% decrease in the sum of the diameters of the target lesion, taking as reference the baseline sum diameters.
 - 7.2.1.3. Progressive Disease (PD) - At least a 20% increase in the sum of diameters of target lesions, taking as reference the smallest sum on study (this includes the baseline sum if that is the smallest on study). In addition to the relative increase of 20%, the sum must also demonstrate an absolute increase of at least 5 mm. (Note: the appearance of one or more new lesions is also considered progression)
 - 7.2.1.4. Stable Disease (SD) - Neither sufficient shrinkage to qualify for PR nor sufficient increase to qualify for PD, taking as reference the smallest sum diameters while on study.

- 7.3 Progression free survival defined with follow-up radiological assessment with progression free survival (PFS) calculated from the point of start of SBRT to the point of recurrence or death.
- 7.4 Overall survival (OS) defined from the point of start of SBRT to the time of death or last follow-up if alive.
- 7.5 Tumor pathology: H&E staining and pathologic evaluation for percentage of viable tumor remaining as measured by the presence of necrosis, fibrosis, hyalinization, and/or calcification, compared to pre-SBRT pathology.

8. Study Parameters

- 8.1 Patients will be followed for a minimum of three years with standard-of-care clinical visits, laboratory studies, and imaging. A study calendar is provided below. After treatment, patients will be seen for clinical follow-up at 1 month after treatment and then every 3 months until 6 months after treatment, at which point the visits will occur every 6 months until 3 years have passed, at which point further follow-up will be at the discretion of the treating physician.

Table 2: Study Calendar

	Pre-treatment (within 6 weeks of reg)	Wk 1	Wk 2	4-6 wk post SBRT	MWA ¹	1 month post MWA	Follow up visits ²
Informed Consent	X						
Biopsy ⁴	X						
MRI Clearance	X						
Radiation planning	X						
SBRT		X	X				
Microwave Ablation					X		
Demographics	X						
Medical History	X	X				X	X
Physical Examination	X		X	X		X	X
Vital Signs	X			X		X	X
Height	X						
Weight	X		X			X	X
ECOG Performance status	X	X	X	X		X	X
Complete blood count with differential count	X		X	X			
Basic Metabolic Panel	X			X		X	X

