Adverse event evaluation		X	X	X		X	X
B-hCG for WOCBP	X						
Research Biopsy ³	X				X		
Radiological evaluation/CT or MRI of Chest, Abdomen and Pelvis	X			X ⁵			X ⁵

¹: MWA will be approximately 8 weeks post XRT

²: Followup: 3 months and 6 months post MWA then every 6 month for 3 years, then annually

³: Research biopsy sampling will be done at the time of the diagnostic biopsy (if not yet performed at time of consent) and at during the microwave ablation procedure

⁴: Clinical diagnostic biopsy does not have a “window”. Patient must be treatment naïve for the renal cell carcinoma at time of study enrollment.

⁵: Imaging post ablation therapy will be at MD discretion, and in accordance with NCCN guidelines

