9.3 Definition of end-points

- 9.3.1 Primary Endpoint of the Phase I study:

Dose-limiting toxicity (DLT) will be defined as grade 4 or higher non-hematologic toxicity attributable to treatment occurring until 30 days after ablation. This will exclude toxicities not caused by treatment, such as pain due to tumor progression. Toxicities will be defined per NCI CTCAE v5.0.

- 9.3.2 Secondary endpoints of the Phase I study:
 - 9.3.2.1 Local control: Radiologic response per RECIST criteria and volumetric measurements.
 - 9.3.2.2 Progression free survival defined with follow-up radiological assessment with progression free survival (PFS) calculated from the point of start of SBRT to the point of recurrence or death.
 - 9.3.2.3 Overall survival (OS) defined from the point of start of SBRT to the time of death or last follow-up if alive.
 - 9.3.2.4 Tumor pathology: H&E staining and pathologic evaluation for percentage of viable tumor remaining as measured by the presence of necrosis, fibrosis, hyalinization, and/or calcification, compared to pre-SBRT pathology.

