13.0 Safety Monitoring

13.1 Adverse Event List for SBRT

Likely

- Gastritis
- Nausea and vomiting
- Diarrhea
- Fatigue
- Loss of appetite and weight loss
- Mild radiation dermatitis

Less likely

- Pigmentation changes and fibrosis in the cutaneous, subcutaneous and deep visceral tissues in the radiation field
- Musculo-skeletal aches in the treatment fields.

Decrease in blood counts resulting in increased risk of infection, weakness, and/ or in bleeding and bruising easily

Hematuria

Rare but serious late effects

Bowel obstruction

Gastric, duodenal or small-bowel ulceration or perforation

Hepatotoxicity

Chronic Kidney Injury

Renal Hemorrhage

Transient myelopathy

Second malignancy

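### No liver tests are scheduled and hepatotoxicity is missing from the late-effect lists, so laboratory-graded hepatic toxicity will be under-ascertained and a low count cannot be read as hepatic safety

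*Combined protocol and SAP*

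**What the plan says.** Laboratory tests are set out in three places.

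- **6.3.2 (baseline):** "Laboratory evaluation including complete blood count (CBC) with differential, basic metabolic panel (BMP) including creatinine".
- **6.8 (follow-up):** "A BMP (including creatinine) will be obtained with imaging to evaluate renal function".
- **Table 2 (study calendar):** the only chemistry row is "Basic Metabolic Panel", marked at pre-treatment, 4-6 weeks post SBRT, 1 month post MWA and the follow-up visits. The other blood tests are a CBC and, for women of childbearing potential, a B-hCG.

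The protocol recognises the liver as an organ at risk. Section 13.1 lists "Hepatotoxicity" for SBRT under the heading "Rare but serious late effects", and Table 1 sets a liver dose-volume limit.

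On analysis, aim 2 in section 1 is to assess early and late toxicity rates. Section 9.4.1 tabulates toxicities by type and grade, and grading follows CTCAE v5.0. Section 9.3.1 defines the DLT as "grade 4 or higher non-hematologic toxicity attributable to treatment occurring until 30 days after ablation".

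**The concern.** The toxicity table is a main product of a phase I trial. Here it also feeds the safety purpose of the Phase IB cohort (9.1.2.1) and the judgement on tolerability that precedes a Phase II study (9.5.1). A laboratory-based hepatic grade needs a laboratory value, and the plan schedules none, before or after treatment.

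Attribution suffers as well. Patients with metastatic disease are eligible (4.1.7), and adjuvant systemic treatment is allowed (6.7). If a liver test is ordered later and is abnormal, there is no scheduled pre-treatment value to compare it with.

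The gap extends to data collection. The protocol classes hepatotoxicity as a late effect, but neither list that governs late toxicity names it. A late hepatic event that is not serious has no scheduled test and no named route into the database.

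**Working it through.** **1. Listed risks against what is measured and collected.** Section 13.1 names seven rare, serious late effects of SBRT.

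| Late effect in 13.1 | Named in 6.8 long-term list | Named in 13.4 list after the 30-day visit | Scheduled blood test |
|---|---|---|---|
| Bowel obstruction | Yes | Yes | Not applicable |
| Gastrointestinal ulceration or perforation | No | Yes | Not applicable |
| Hepatotoxicity | No | No | None |
| Chronic kidney injury | Yes (as nephrotoxicity) | Yes (as nephrotoxicity) | BMP with creatinine |
| Renal hemorrhage | No | No | CBC, not after the 4-6 week visit |
| Transient myelopathy | No | Yes | Not applicable |
| Second malignancy | No | Yes | Not applicable |

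Five of the seven have a counterpart in 13.4. Hepatotoxicity and renal hemorrhage do not, and of these two hepatotoxicity is the one with no relevant blood test at any time.

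**2. Chemistry draws.** Table 2 gives baseline, 4-6 weeks post SBRT and 1 month post MWA (3). Footnote 2 gives 3, 6, 12, 18, 24, 30 and 36 months (7). The total is 3 + 7 = 10 per patient through 36 months, none with a liver test. The count is approximate, because 6.8 ties follow-up BMPs to imaging and footnote 5 leaves post-ablation imaging to the physician's discretion.

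**3. What a count of zero can show.** The plan states no hepatotoxicity rate, so it has no figure to reproduce. The sample sizes do agree: 3 levels × 3 to 6 patients = 9 to 18, and 18 + 10 = 28.

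Let p be the true rate and s the share of cases found without scheduled liver tests. The recorded rate is q = p × s, and the chance of recording no case in n patients is (1 − q)^n. The values of p and s below are assumptions.

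| p | n | s = 1 (full testing) | s = 0.25 |
|---|---|---|---|
| 1% | 3 | 0.99^3 = 97.0% | 0.9975^3 = 99.3% |
| 1% | 6 | 0.99^6 = 94.1% | 0.9975^6 = 98.5% |
| 5% | 3 | 0.95^3 = 85.7% | 0.9875^3 = 96.3% |
| 5% | 6 | 0.95^6 = 73.5% | 0.9875^6 = 92.7% |

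At these rates, zero cases in one dose level is the likeliest result even with full testing.

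The difference lies in what a zero then means. With no cases in n patients, the one-sided 95% upper bound for q is 1 − 0.05^(1/n). If 6 Phase IA and 10 Phase IB patients are treated at the MTD, n = 16 and the bound is 17.1%. The bound for p is 17.1% / s:

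- s = 1: 17.1%
- s = 0.5: 34.2%
- s = 0.25: 68.4%

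As s falls further, the bound becomes uninformative. The plan gives no means of estimating s for asymptomatic laboratory toxicity, so a recorded zero gives no usable bound for it.

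**The case against.** The other side has several good points.

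- **Clinical detection remains.** Table 2 schedules "Adverse event evaluation" in weeks 1 and 2, at 4-6 weeks post SBRT, at 1 month post MWA and at follow-up visits, with physical examinations and imaging as well. Section 6.8 also permits "Any other evaluations prompted by symptoms, laboratory evaluation, or at the treating" physicians' discretion. Under 13.4, related serious adverse events are collected for up to three years after MWA. A reader might infer that hepatotoxicity cannot be graded at all. That goes too far: the loss is confined to laboratory-based grades, mainly asymptomatic or lower-grade changes.
- **The event is called rare and late.** A reader might infer that the missing tests will produce near-zero counts at every dose level. The documents do not support that cause. They give no rate, and few or no cases are expected at 3 to 6 patients per level even with full testing.
- **Exposure is limited.** The liver constraint is the same at all three dose levels, and patients whose plans cannot meet the constraints continue off study (6.4.6). Escalation therefore does not mean unrestricted liver dose.
- **The DLT effect is conditional.** A reader might infer that escalation could pass over an unseen hepatic DLT. Section 6.2.2 gives a named list of DLT events without hepatic toxicity, while 7.1.1 and 9.3.1 are worded broadly enough to include it. The window closes 30 days after MWA, although the protocol classes hepatotoxicity as late. The effect depends on which definition applies.
- **Baseline imaging exists.** It gives some context on liver metastases, but it does not replace a baseline laboratory value.

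These points narrow the concern. They do not supply the missing baseline and on-study values or the missing entries in 6.8 and 13.4.

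**Conclusion.** The point holds in a limited form. The protocol names a hepatic risk and plans around it, but schedules no liver test and leaves hepatotoxicity off both late-toxicity lists. Laboratory-graded, asymptomatic or lower-grade hepatic toxicity will be under-ascertained, and abnormal values found by chance will lack a baseline for attribution. A low count in the 9.4.1 table would not show hepatic safety.

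The size of the shortfall cannot be derived from the documents, and the rates and detection shares used above are illustrations only. Any effect on the primary endpoint is secondary. Sections 6.2.2, 7.1.1 and 9.3.1 must be reconciled before it can be stated.

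The conclusion rests on one assumption: that a BMP carries its usual meaning, without liver tests. The documents say only that it includes creatinine. The change is still worth making because it is cheap and a baseline value cannot be recovered after treatment.

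**What to change.** - In 6.3.2, 6.8 and Table 2, replace the basic metabolic panel with a comprehensive metabolic panel (adding AST, ALT, alkaline phosphatase, bilirubin and albumin) at the draws already scheduled. At a minimum, do so at baseline, 4-6 weeks post SBRT and 1 month post MWA.
- Grade hepatic values by CTCAE v5.0 against the baseline value.
- Add hepatotoxicity to the long-term toxicities in 6.8 and to the effects collected after the 30-day visit in 13.4. Without this, late values would have no named collection route.
- In 9.4.1, tabulate worst hepatic grade by dose level, with the number of patients who had a baseline and at least one later value.
- Reconcile the DLT definitions in 6.2.2, 7.1.1 and 9.3.1, so that it is clear whether hepatic events count.

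The cost is a wording change and a small assay fee, with no extra visit or needle stick. Some abnormal values will come from metastases or systemic drugs, and the baseline value helps to sort these out.

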6.4 Radiotherapy details

6.4.1. Simulation

All patients will be planned using MRI simulation on the MRIdian system (Viewray Inc., Mountain View, CA). Simulation scans will be performed with patients supine in the arms up or down position. MRI coils will be placed directly on the patient. Patients will be simulated with a breath hold technique. A standard-of-care computed-tomography (CT) planning scan will be obtained in the same position as the MRI planning scan in order to obtain density data for dose calculations. The MRI and CT planning scan will then be imported in to the Treatment Planning System (TPS) (Viewray Inc., Mountain View, CA) which will then be utilized to create SBRT treatment plans.

6.4.2. Target Delineation

Gross tumor volume (GTV) will be contoured with the help of co-registered pretreatment imaging. No expansion to a clinical tumor volume (CTV) will be performed. A planning tumor volume (PTV) will be customized for each patient at the time of simulation to account

for each patient’s ability to breath-hold, reproducible tumor motion, and estimated variation in daily setup.

6.4.3. Radiation Dose

The PTV will be treated to a dose of 6, 8, or 10 Gy for 5 fractions, for a total dose of 30, 40, and 50 Gy, respectively as per current dose cohort.

6.4.4. Radiation fractionation

Radiation treatments will be delivered on alternate days. Treatments will preferentially start on Mondays, although the start of therapy on Tuesday or Wednesday is also acceptable.

6.4.5. SBRT Planning Process

An inverse IMRT planning process will be performed using the treatment planning system to determine if the desired PTV dose is feasible to administer without exceeding a safe radiation dose to normal structures.

6.4.6. Normal Tissue Constraints

No volume outside of the PTV should receive more than 105% of the prescription dose. Planning dose-volume constraints (Table 1) are based on constraints used by Hong et al.[14] as well as Pham et al[12]. If dose constraints are unable to be met for a given patient at the current dose level, the dose per fraction will be decreased until acceptable constraints are met and the patient will continue off study. Of note, no specific dose constraints will be utilized for the involved kidney. This has been most extensively studied in a series of patients who underwent SBRT to a solitary kidney, with no reports of late toxicity noted[15]. As a result, the QUANTEC group guidelines recommend no specific dose constraints be applied to the involved kidney during SBRT[16].

Structure	Dose Constraint
Spinal Cord	Dmax = 25 Gy
Stomach	D0.1cc < 32 Gy
Bowel	D0.1cc < 32 Gy
Liver	D700cc < 15 Gy
Contralateral Kidney	V13 < 30%, Mean < 10 Gy

Table 1: SBRT Dose Constraint Table

6.5 Microwave ablation (MWA)details

All procedures will be performed under sedation utilizing ultrasound and computed tomography (CT) guidance for percutaneous antenna placement and confirmation. A multidisciplinary team, consisting of a radiologist and a urologist experienced in tumor ablation, will perform each procedure. Depending on the size and location of the tumor, one to three antennas (Certus 140; NeuWave Medical, Madison, WI) will be used. The MW

system used for this study is the Certus 140 (NeuWave Medical, Inc., Madison, WI). The system is an FDA-approved, high-powered (140W in up to three channels) third-generation MW device that uses CO₂ gas cooling to prevent shaft heating. The gas cooling also allows the probes to be stuck into tissue by creating a small ice ball at the tip using the Joule–Thomson method, similar to the tissue cooling mechanism of cryoablation systems. The probes are 17-gauge, and several different ablation zone configurations are available depending on which probe is selected. The expected ablation diameter in ex vivo tissue is available on the manufacturer’s website (www.neuwave.com), but varies somewhat depending on the tissue type and tumor vascularity. If the tumor is in close proximity to adjacent structures, injectable grade dextrose 5% sterile water will be instilled through a spinal needle to increase the distance from the treatment zone (hydrodisplacement). For hydrodisplacement, the treatment team will consider the subjective proximity of structures as well as the expected ablation zone, which varies according to the manufacturer’s specifications for the individual probe types. An ablation protocol utilizing the 65W power setting for 5 minutes will be used in the majority of patients. Ultrasound will be used for real-time monitoring of the extent of ablation to achieve a 5mm margin beyond the tumor, and immediate post-procedure imaging performed using contrast-enhanced CT (CECT) for all patients with adequate renal function. All patients will be admitted overnight for observation as per standard of care.

6.6 Tissue Sampling

Clinical pathologic evaluation

At the time of the initial diagnostic biopsy, a four quadrant biopsy will be performed per normal procedures. All tissue from the four quadrant biopsy will be processed per normal UW pathology procedures.

Research tissue sampling

If a clinical biopsy confirming renal cell cancer has not yet been performed, at the time of the clinical biopsy, 3 additional core biopsy samples will be obtained for research purposes. The samples will allow for creation of paraffin embedded, cryo-embedded and fresh frozen sections for evaluation of SBRT treatment response prior to microwave ablation.

During the microwave ablation procedure, 3 core biopsy samples will be obtained for research purposes. The primary tumor will be assessed for percent residual viable cells, the ratio of residual viable tumor to parenchyma, ratio of fibrotic stroma to tumor mass in the resected specimen, and immune cell infiltration, by the study team at a later date.

The research samples will be obtained and stored by the University of Wisconsin Carbone Cancer Center Translational Science BioCore (TSB-BioBank, University of Wisconsin Hospital Carbone Cancer Center, [name]). The BioBank utilizes ONCORE for “registration” of the samples to the BioBank. Actual samples study samples(research core samples) will be coded with the study number, case # assigned by Radiation Oncology staff, and timepoint: 1 (pre-treatment) or 2 (post- XRT). All BioBank staff have undergone required human subjects training and HIPAA training. Actual specimens will be located within the BioBank in a room that is card access controlled with monitoring.

6.6.1. Permitted Supportive Therapy

All supportive therapy for optimal medical care will be given during the study period at the discretion of the attending physician(s) within the parameters of the protocol and documented on each site's source documents as concomitant medication

6.7 Duration of Therapy

Treatment with SBRT will be delivered over a period of two weeks, with radiation delivered two to three times per week. Four to six weeks after treatment, patients will be evaluated for microwave ablation by the treating radiologist with repeat CT or MRI imaging of the abdomen. Eight weeks after the conclusion of radiation treatment, patients will undergo microwave ablation, a single procedure. Adjuvant systemic treatment will be administered per institutional policies, physician recommendations, and patient preferences. Criteria for removal from study are described below.

6.8 Duration of Follow-Up: Refer to Table 2

After study enrollment, patients will undergo SBRT over a period of approximately 2 weeks. After 8 weeks, patients will undergo microwave ablation. Post treatment, patients will be followed as per standard of care. This will include a clinical visit four weeks after ablation, three months after ablation, six months after ablation, followed by visits every 6 months for a period of 3 years. Imaging will include either contrast-enhanced CT or MRI imaging at 3 and 6 months post therapy and every 6 months for 3 years. A BMP (including creatinine) will be obtained with imaging to evaluate renal function. Long term toxicity (specifically, nephrotoxicity, bowel obstruction, skin changes, and pain) will be assessed at these follow-up visits. Follow-up visits will be conducted by one of the treating physicians (radiation oncologist, interventional radiologist, or urologist) who will document physical exam, laboratory, and imaging findings as well as evaluate for toxicity. Any other evaluations prompted by symptoms, laboratory evaluation, or at the treating physicians' discretion may be performed as per standard of care. If a patient decides to withdraw from the study for non-treatment related reasons, no additional study-specific information will be obtained from the patient's future follow-up visit.

